COMIRB Protocol
COLORADO MULTIPLE INSTITUTIONAL REVIEW BOARD
[name] [contact] [contact]-
[name]

Protocol #: COMIRB 15-0036

**Project Title: Use of Ultrasonic Bone Scalpel in Adolescent Idiopathic Scoliosis – Randomized
Clinical Trial**

Principal Investigator: [name]

Version Date: 7/6/2015

I. Hypotheses and Specific Aims:

The primary purpose of this randomized trial is to compare the efficacy of an ultrasonic bone scalpel (or osteotome device) with standard of care surgical instruments during posterior spine fusion with instrumentation. The primary outcome variable in this trial is estimated blood loss per spine level fused (EBL/level). Secondary outcome variables include the probability of meeting the intraoperative blood transfusion criteria, incidence of adverse events, and incidence of surgical site infections. Subjects with adolescent idiopathic scoliosis undergoing planned posterior spinal fusion with instrumentation will be recruited from a single tertiary recruitment center for this trial.

Primary Aim 1: Compare estimated blood loss per level fused

Hypothesis 1: The average estimated blood loss per level fused will be significantly lower in the ultrasonic bone scalpel (USBS) group compared to the standard of care group.

Secondary Aim 1: Compare the incidence of adverse events in the two groups.

Hypothesis 2: There will be no difference in the incidence of adverse events in the bone scalpel group compared to the standard of care group.

Secondary Aims 2-3: Compare the proportion of patients meeting intra-operative blood transfusion criteria in the two groups.

Hypothesis 3: The proportion of subjects meeting the intra-operative blood transfusion criteria will be significantly lower in the bone scalpel group compared to the standard of care group.

II. Background and Significance:

Adolescent idiopathic scoliosis (AIS) is a common spine deformity in children. In severe cases posterior spinal fusion surgery (PSF) is indicated to correct the deformity and prevent curve progression. Due to the duration and invasiveness of this procedure, PSF is associated with high intraoperative blood loss. On average, AIS patients typically lose 65-150 mL per vertebral level during spinal fusion surgery.[1] With regard to total blood volume, AIS patients typically lose 25-30% of their total blood volume during PSF.[1, 2] The percent of patients who receive an

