Estimated blood loss/level [^]
Secondary Clinical Outcomes
Intraoperative and postoperative complications (events that cause a deviation from routine care) ^{^†‡}
Probability of meeting blood transfusion criteria (see section) ^{^†}
Procedure Time (first incision to close) [^]

Demographics/Covariates (potential confounding variables)	
Age at surgery*	BMI percentile at surgery*
Gender at surgery*	Weight (kg) at surgery*
Exposure to second hand smoke*	Preoperative Lenke Classification*
Preoperative major Cobb angle*	Preoperative hemoglobin/hematocrit*
Postoperative major Cobb angle††	Postoperative hemoglobin/hematocrit†
Intraoperative use of intrathecal narcotics^	Donor hematocrit^
Vertebral levels fused^	Intraoperative use of antifibrinolytic^

Exploratory Variables	
Unplanned return to OR††	Surgical site infection†
Procedure Time^	

* Collected preoperatively or day of surgery (before surgery)

^ Collected intraoperatively

† Collected postoperatively: short term follow-up, during initial hospital stay

‡ Collected postoperatively: long term follow-up, one year postoperative

I. Description of Population to be Enrolled:

All patients with a diagnosis of Adolescent Idiopathic Scoliosis who are scheduled for spinal fusion surgery and meet the following criteria will be eligible to participate in the study:

Inclusion Criteria:

1. 10-18 years of age
2. Diagnosis of AIS
3. Scheduled for a posterior spinal fusion (without Schwab Grade II or higher osteotomy)

Exclusion Criteria:

1. Plan for a posterior column osteotomy of Schwab Grade II or higher
2. Prior spinal surgery
3. MRI abnormalities (such as syrinx and/or chiari malformations)
4. Subjects with medical comorbidities (e.g. heart, lung, kidney disease)
5. Subjects with bleeding diatheses
6. Non-idiopathic etiology for scoliosis

II. Study Design and Research Methods

a. Power Analysis

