EBL will be calculated in the following manner: First, the total fluid volume will be calculated: The volume of the contents of all of the blood and fluid canisters used during the course of the surgical procedure will be recorded based on the photographs. To this we will add the cell saver intake fluid, taken from a report generated by the cell saver system. Next, the total irrigation volume used during surgery will be calculated. The irrigation volume will be estimated as the difference in volume of the irrigation bag at surgery cut versus surgery close. For subjects in the USBS group, the total irrigation volume will also include the difference in volume of the USBS irrigation bag at surgery cut versus surgery close. Estimated blood volume will be calculated as total fluid volume minus irrigation volume.

Method 3:

To validate the above described method 2, the study personnel will also use the same method of calculated blood loss as was used in a study by Da Cunha et al (2015).[22] The blood loss calculation from this study was adapted from the method proposed in Brechter et al (1997).[23] This method calculates blood loss through the following mathematical model:

$$EBL = [EBV * (Hb_{pre} - Hb_{post}) / Hb_{pre}] + [Donor RBC_{normalized}] + [Cell Salvage RBC_{normalized}]$$

Where:

EBV = Estimated Blood Volume = Patient Weight (kg) x 70 ml/kg

Hb_{pre} = preoperative patient Hemoglobin

Hb_{post} = postoperative Day One Patient Hemoglobin

Donor RBC_{normalized} = [donor RBC volume] x [(donor Hct) / (Hct_{pre} + Hct_{post}) / 2]

Cell Salvage RBC_{normalized} = [cell saver RBC volume] x [(cell saver Hct) / (Hct_{pre} + Hct_{post}) / 2]

Hct_{pre} = Preoperative Patient Hematocrit

Hct_{post} = Postoperative Patient Hematocrit

Patient's weight will be measured the day of surgery. Hct_{pre} and Hb_{pre} will be taken by the lead anesthesiologist prior to first incision through an ISTAT. Hct_{post} and Hb_{post} will be taken 12-18 hours after the end of the procedure through an ISTAT. Donor and cell saver Hct will be taken by the lead hematologist before bags are sent up to the OR.

f. Intraoperative Transfusion Guidelines

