Traditionally, CHCO does not have strict transfusion protocols for patients undergoing posterior spinal fusion surgery. Often these decisions are made at the discretion of the anesthesia provider in the operating room. This is due to the care involved and the differences between cases when caring for these incredibly complex patients. This is further complicated by differences in diagnosis, osteotomy procedures, and severity/flexibility of the scoliosis. Often in these complex surgeries, intangible variables such as estimated time remaining, perceived rate of blood loss, and trend of hematocrit levels all factor in to the decision. However, for this study, we have established guidelines for determining the need for intraoperative transfusion. The study team feels comfortable with these guidelines because all enrolled patients in this study will have a consistent diagnosis of adolescent idiopathic scoliosis, low rates of intraoperative bleeding, and no complex osteotomies such as a vertebral column resection. Our guidelines are below:

- Hematocrit will be checked every 30 minutes by the anesthesiologist
- Hematocrit levels below 23% will trigger a transfusion
- Hematocrit levels between 23-28% will trigger a transfusion if hypotension and/or tachycardia (>20% different from baseline) is present despite adequate fluid resuscitation

g. Study Interventions and Follow Up:

After patients have enrolled in the study and been randomized to a treatment group, study interventions will take place. The above outcomes will be collected at three different time points: preoperatively, intraoperatively, and postoperatively. Depending on the treatment randomization assignment, patients will undergo surgery with either the powered ultrasonic bone scalpel or with standard of care orthopedic surgical tools such as curettes, rongeurs, or high-speed burrs. These tools will be used in either treatment group for superior and inferior facetectomies, as well as to aid exposure of the pedicle for screw placement. All of these tools are commonly used at CHCO by facility pediatric orthopedic surgeons. Selection is most commonly made based on surgeon preference and familiarity. All surgeons involved in this study routinely use the surgical instruments being investigated. They have all received training and have experience with these instruments.

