An intent to treat analysis of all randomized subjects will be performed. Descriptive statistics will be used to compare the distribution of demographics and clinical characteristics in the two groups. Baseline covariates significantly different between groups will be considered as potential confounding variables in subsequent statistical models. The primary aim of this study is to compare differences in estimated blood loss per fusion level (EBL/level) between the USBS and standard of care groups ($\theta = \theta_{USBS} - \theta_{standard\ care}$). We aim to test the null hypothesis that the difference between groups is less than or equal to 0 ($H_0: \theta \geq 0$). An independent sample t-test or multiple variable linear regression analysis, as appropriate, will be used to compare total EBL/level in the two study groups. For the secondary outcome variables, Chi-square tests will be used to compare differences in the categorical variables (the risk of adverse events, proportion of subjects meeting the intra-operative blood transfusion criteria) between the groups. Independent sample t-tests or Wilcoxon rank sum tests will be used to compare differences in the continuous variables (operative time, post-operative length of stay, and intraoperative irrigation volume).

e. Trial Monitoring/Human Subjects Research Consideration

Data Safety and Quality - All data will be collected and stored in a REDCap database. Access to the database will be restricted to investigators involved the study protocol per study personnel section of the COMIRB protocol application and/or the study delegation of duties log. Photographs obtained during surgery will be de-identified, assigned an appropriate study ID and will be stored on a secure departmental server that is managed by the IT department at Children's Hospital Colorado. The study coordinators will review data stored in the REDCap database on an ongoing basis. Potential outliers and/or biologically implausible data points will be identified and reviewed on an individual basis with the Principal Investigator.

Safety Monitoring – Based on the advice of our clinical trial study design consultant, [name], a Data Safety Monitoring Board (DSMB) will review the safety and efficacy of the study. The DMSB will consist of an orthopaedic surgeon not directly

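### The transfusion-criteria endpoint is tested with an unadjusted chi-square, although preoperative hematocrit and weight are already collected; pre-specified adjustment would give a modest gain in precision

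*Combined protocol and SAP*

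**What the plan says.** Hypothesis 3 (Hypotheses and Specific Aims) is directional: "The proportion of subjects meeting the intra-operative blood transfusion criteria will be significantly lower in the bone scalpel group" than in the standard-care group.

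The Intraoperative Transfusion Guidelines define the criteria in two limbs. The first is "Hematocrit levels below 23% will trigger a transfusion". The second is "Hematocrit levels between 23-28% will trigger a transfusion if hypotension and/or tachycardia (>20% different from baseline) is present despite adequate fluid resuscitation".

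The Data Analysis Plan assigns this endpoint to the sentence "Chi-square tests will be used to compare differences in the categorical variables". It offers linear regression as an option for EBL/level and names no model for a binary outcome. Its one general rule on covariates is "Baseline covariates significantly different between groups will be considered as potential confounding variables in subsequent statistical models".

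The covariate table under Outcome Measure(s) lists "Preoperative hemoglobin/hematocrit" and "Weight (kg) at surgery", both marked as collected before surgery. Method 3 of the blood-loss section uses the same quantities: "EBV = Estimated Blood Volume = Patient Weight (kg) x 70 ml/kg", preoperative hemoglobin in the main term, and preoperative hematocrit in the red-cell normalisation.

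**The concern.** Whether a patient reaches either limb depends on the starting hematocrit and on the fraction of blood volume lost. For a given loss in mL, that fraction depends on weight. Both baseline values should therefore predict the endpoint, and a test that ignores them leaves predictable variation between patients in the error term.

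The covariate rule does not repair this. Under randomisation a 5% baseline test flags any given covariate about 5% of the time, however prognostic it is. For two roughly independent covariates, neither is flagged in about 0.95 × 0.95 = 90% of trials. When one is flagged, the plan says only that it will be considered, and gives no binary-outcome model to put it in.

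At stake is the precision of a secondary efficacy comparison with about 31 patients per arm.

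**Working it through.** **1. The plan's own figure.** The documents give no power for this endpoint. The stated sample size is for EBL/level, and it reproduces. With pooled variance (28² + 30²)/2 = 842 and a difference of 24, n per arm = 2 × 842 × (1.960 + 1.2816)² / 24² = 30.7, so 31 per arm and 62 in total. With the two stated boundaries (2.7965 and 1.9774), power is 90.1%.

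**2. Power of the planned chi-square at 31 per arm.** With p̄ the mean of the two proportions:

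power = Φ{ [ |p₁ − p₂| − 1.96 √(2p̄(1 − p̄)/n) ] / √([p₁(1 − p₁) + p₂(1 − p₂)]/n) }

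| Standard vs USBS | Power |
|---|---|
| 30% vs 20% | 14.5% |
| 25% vs 12% | 25.8% |
| 50% vs 29% | 39.2% |
| 75% vs 50% | 53.0% |

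The Background cites transfusion rates from 20-30% up to 50-75%. The pairs above are illustrations; the documents give no expected rates by arm.

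**3. Are the two covariates prognostic?** The model used is lowest Hct = Hct_pre × exp(−EBL/(70 × weight)) × (1 − dilution) + noise. EBL/level comes from the Power Analysis (72, SD 28; 48, SD 30). Assumed, not in the documents: 11 levels, Hct_pre 39 (SD 3), weight 54 kg (SD 11), 10% dilution, noise SD 1. Without noise, at the means:

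- Standard: EBL = 72 × 11 = 792 mL; blood volume = 70 × 54 = 3,780 mL; lowest Hct = 39 × exp(−0.2095) × 0.9 = 28.5.
- USBS: EBL = 48 × 11 = 528 mL; lowest Hct = 39 × exp(−0.1397) × 0.9 = 30.5.
- Standard, Hct_pre one SD lower (36): 26.3.
- Standard, weight one SD lower (43 kg): 27.0.

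One SD of starting hematocrit moves the lowest value by 2.2 points and one SD of weight by 1.5, against 2.1 between the arms. On these assumptions both are prognostic for hematocrit. Whether that carries through to the binary endpoint depends on the rule.

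**4. Power, chi-square against a linear risk-difference model with arm, Hct_pre and weight (simulated, 31 per arm).**

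| Definition of the event | Chi-square | Adjusted |
|---|---|---|
| Single cut-off as proxy, 44% vs 23% | 42% | 54% |
| Same, Hct SD 4 | 35% | 48% |
| Same, Hct SD 2 | 50% | 57% |
| Single cut-off, 24% vs 11% | 28% | 32% |
| Single cut-off, 14% vs 6% | 18% | 17% |
| Two limbs, sign probability 25%, dilution 10% | 17% | 16% |
| Two limbs, sign probability 50%, dilution 10% | 24% | 25% |
| Two limbs, sign probability 25%, dilution 20% | 26% | 28% |
| Two limbs, sign probability 50%, dilution 20% | 31% | 33% |
| Below-23% limb only, dilution 10% | 7% | 7% |
| Below-23% limb only, dilution 20% | 26% | 30% |

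The two-limb rows treat the haemodynamic sign as independent of hematocrit. Making it more likely with larger fractional blood loss (eight settings) gave gains of 0 to 7 points, 2 to 4 in six of them. A further set of runs gave about 0 to 6 points for the two-limb rule and about −1 to +9 for the below-23% limb alone. With 4,000 runs, the simulation error of a power near 30% is √(0.3 × 0.7/4000) = 0.7 points, so differences of a point or so are noise.

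**5. Type I error.** The adjusted linear test ran at 4.7-5.9%. An unpenalized logistic likelihood-ratio test ran at 5.3-7.6%.

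**The case against.** The strongest objection is about size. The 12-point gain (42% to 54%) appears only when the protocol's rule is replaced by a single cut-off. A cut-off at 28 counts every patient below 28% as an event, whereas the protocol requires a haemodynamic sign in the 23-28% band. Once that sign is modelled it adds variation that hematocrit and weight explain poorly, and most of the gain disappears. This stands. The inputs are also assumptions, and the transfusion section expects low rates of intraoperative bleeding in these patients, which points towards event rates where adjustment gains nothing. This stands too, although the literature range in the Background leaves higher rates possible.

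It is also fair to say that the plan is not silent on adjustment. The baseline-difference rule exists, but it screens for chance imbalance, so this answers the concern only in part.

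Three stronger readings are tempting, and the documents support none of them.

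- A reader might infer that the chi-square is wrong or biased. With 1:1 randomisation it is a valid test of the difference in proportions.
- A reader might infer that adjustment would make Hypothesis 3 adequately powered. No power is claimed for this endpoint, and power stayed at or below about 61% in every adjusted scenario, including those with a single cut-off.
- A reader might look to a continuous analysis of lowest hematocrit for support. That is a different endpoint, and its power says nothing about the test of this one.

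**Conclusion.** The point holds as a modest loss of precision. The plan tests a hematocrit-dependent endpoint without using two baseline predictors that it already collects, and its covariate rule does not choose covariates by how well they predict the outcome.

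The expected gain from adjustment at 31 per arm is about 0 to 6 power points under the two-limb rule and up to about 9 if only the below-23% limb applies. Gains of about 11 points or more appeared only where the criteria acted as a single cut-off at 26-28%. At low event rates there is none. These figures rest on assumed levels fused, hematocrit and weight distributions, dilution and probability of a haemodynamic sign, so they are a range and not a forecast. The change is worth considering; the validity of the trial does not depend on it.

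**What to change.** In the Data Analysis Plan, pre-specify for the transfusion-criteria endpoint:

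- a standardized (covariate-adjusted) risk difference with 95% CI, from a model with arm, preoperative hematocrit and weight, and no covariate selection after the data are seen;
- a test that is safe in small samples: a linear risk-difference model with a t reference or robust standard errors, or a penalized logistic model;
- which preoperative hematocrit measurement is used;
- the crude proportions and the chi-square as supporting results.

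No extra patients, visits or measurements are needed. There are two costs. The covariate list must stay short: at 25% vs 12% only about 31 × 0.25 + 31 × 0.12 = 11 to 12 events are expected. And an unpenalized logistic likelihood-ratio test should be avoided because of its inflated type I error. The endpoint and the transfusion guidelines themselves stay as they are.

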Probability of Stopping at the Interim Analysis To aid in the interpretation of the stopping criteria, the probability of stopping the trial at the interim analysis (for benefit or harm), under hypothetical scenarios in which theta is known, has been estimated in the table below.

True θ	Probability of Stopping for Harm	Probability of Stopping for Benefit
---------------	----------------------------------	-------------------------------------

-29	0.4930	0.0000
-14	0.0729	0.0000
0	0.0050	0.0050
14	0.0000	0.0729
29	0.0000	0.4930

Power/Type I Error Rate The power and type I error rate associated with this group sequential design, under hypothetical situations in which theta is known, is outlined in the table below.

True θ	Power for Lower Rejection Boundary	Power for Upper Rejection Boundary
-29	0.975	0.000
-14	0.470	0.000
0*	0.025	0.0250
14	0.000	0.470
29	0.000	0.975

*Under null hypothesis ($\theta = 0$), the design maintains a type I error rate of 0.05.

f. Summarize Knowledge to be Gained

This study will help to identify any potential advantages and disadvantages with regard to the use of an ultrasonic bone scalpel used in posterior spinal fusion surgery for patients diagnosed with Adolescent Idiopathic Scoliosis. A better understanding of the intraoperative outcomes such as estimated blood loss and surgical time compared between the two groups could reveal if one technique is able to provide significantly better results during surgery. If one method is determined to be more effective or efficient than the other, then it could have a positive impact on spinal fusion surgery. Decreased blood loss could lead to decreased need of intraoperative and postoperative transfusions and the risks associated with them. Further, shorter operative time would decrease wound exposure time, which could have an effect on postoperative complications. Decreased operative time could also decrease the financial burden of surgery.

V. References

1. Shapiro, F. and N. Sethna, *Blood loss in pediatric spine surgery*. Eur Spine J, 2004. **13 Suppl 1**: p. S6-17.
2. Thompson, M.E., et al., *Predicting excessive hemorrhage in adolescent idiopathic scoliosis patients undergoing posterior spinal instrumentation and fusion*. Spine J, 2014. **14(8)**: p. 1392-8.

3. Diab, M., et al., *Use and outcomes of wound drain in spinal fusion for adolescent idiopathic scoliosis*. Spine (Phila Pa 1976), 2012. **37**(11): p. 966-73.

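### Operative time is compared without adjustment although surgeon, gender and preoperative Cobb angle are already recorded; prespecifying them would probably sharpen a valid but less precise analysis

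*Combined protocol and SAP*

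**What the plan says.** The Outcome Measure(s) section lists "Procedure Time (first incision to close" among the secondary clinical outcomes, and lists procedure time again among the exploratory variables. I take this to be the operative time of the analysis plan. It is total elapsed time, and no unit is given.

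The Data Analysis Plan handles three continuous variables together ("operative time, post-operative length of stay, and intraoperative irrigation volume"): "Independent sample t-tests or Wilcoxon rank sum tests will be used to compare differences in the continuous variables". No covariate is named for any of them. Regression is offered only for the primary outcome: "An independent sample t-test or multiple variable linear regression analysis, as appropriate, will be used to compare total EBL/level in the two study groups".

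One general rule on covariates comes earlier in the same section: "Baseline covariates significantly different between groups will be considered as potential confounding variables in subsequent statistical models".

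The covariate table marks gender and major Cobb angle as collected before surgery, and "Vertebral levels fused" as collected intraoperatively. Under Randomization and Blinding, blocks are built on surgeon and gender. The section on knowledge to be gained attaches possible benefits to a time saving: "shorter operative time would decrease wound exposure time, which could have an effect on postoperative complications".

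**The concern.** Operative time is likely to vary with the surgeon and with the size of the deformity, whichever instrument is used. In an unadjusted comparison that variation stays in the error term. At about 31 per arm the interval for the time difference will be wide, and the plan leaves aside preoperative information that could narrow it.

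The general covariate rule does not close the gap, for two reasons. It depends on a significant baseline difference, so when the arms are balanced it does nothing and the precision is not recovered. It also refers to later models, and no model is specified for operative time.

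What is at stake is the width of one interval for a lower-tier outcome. The protocol does intend to draw on that outcome when it discusses wound exposure and cost.

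**Working it through.** **Plan's own figure.** The documents give no SD, effect size or power for operative time, so there is nothing to reproduce for this outcome. The only related figure is the sample size for blood loss per level: difference 24 mL/level, SDs 28 and 30, two-sided alpha 0.05, power 90% (Power Analysis). The mean variance is (28² + 30²)/2 = 842. Then n = 2 × (1.960 + 1.282)² × 842 / 24² = 30.7, that is 31 per arm. With the stated two-stage bounds (2.7965 and 1.9774) the power is 90.06%. The 31 per arm is confirmed, but it says nothing about operative time.

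**Unadjusted precision at 31 per arm.** In units of the operative-time SD, the difference detectable with 80% power is (1.960 + 0.842) × √(2/31) = 0.71 SD. Power for a 0.5 SD difference is 50%.

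**Effect of adjustment.** Let R² be the share of within-arm variance in operative time that surgeon, gender and Cobb angle explain together. It is an assumption, because the documents give no value. The standard error is multiplied by about √(1 − R²) and by a small penalty for fitting covariates.

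| Assumed R² | √(1 − R²) | SE ratio with penalty | Implied penalty | SE reduction | Detectable at 80% (0.712 × ratio) |
|---|---|---|---|---|---|
| 20% | 0.894 | 0.93 | 0.93/0.894 = 1.04 | 7% | 0.66 SD |
| 30% | 0.837 | 0.87 | 0.87/0.837 = 1.04 | 13% | 0.62 SD |
| 40% | 0.775 | 0.80 | 0.80/0.775 = 1.03 | 20% | 0.57 SD |

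**Break-even.** Adjustment helps only if √(1 − R²) × penalty is below 1. For a penalty of 1.035, R² must exceed 1 − 1/1.035² = 6.6%. For 1.04, it must exceed 1 − 1/1.04² = 7.5%. Hence about 7%.

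**Is that penalty reasonable?** With two surgeons, the three covariates use one degree of freedom each. The usual approximation for variance inflation from chance imbalance is 1 + p/(N − p − 3). With p = 3 and N = 62 this is 1 + 3/56 = 1.054, or 1.026 on the SE scale. The 4% used above is therefore somewhat cautious. If the trial stops at the interim with 16 per arm, the same formula gives 1 + 3/26 = 1.115, or 1.056 on the SE scale, and the break-even rises to 1 − 1/1.115 = about 10%.

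**The case against.** The strongest reply is that nothing here is wrong. Allocation is 1:1 and randomised, the two-sample test is unbiased, and its standard error already includes variation from case mix. That stands. A reader might infer that chance imbalance makes the planned result misleading, but false positives from imbalance are exactly what the test's type I error rate covers.

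A second reply is that the plan already provides for covariates. This stands in part. The rule could bring in Cobb angle after a marked imbalance, so it would be unfair to say that covariates are ignored. It does not serve precision, and it lets the data choose the model.

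A third reply is that the outcome matters little. This also stands. Procedure time is absent from the aims and from the secondary outcomes named in the opening section, it is listed as both secondary and exploratory, and it has no part in the stopping rules.

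Two stronger readings are tempting, and the documents support neither.

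- **That time should be put on a per-level basis, as blood loss is** ("The primary outcome variable in this trial is estimated blood loss per spine level fused (EBL/level"). The stated reasons for interest in time, wound exposure and cost, concern total time. Levels fused is recorded intraoperatively, after allocation. A ratio can also add noise: its relative variance compared with that of time alone is (CV_T² + CV_L² − 2ρ·CV_T·CV_L)/CV_T². With assumed CVs of 0.20 for both and ρ = 0.3, this is (0.04 + 0.04 − 0.024)/0.04 = 1.4, which is 40% more.
- **That differences in levels fused put a known number of minutes of noise into the result.** Assuming an SD of 1.5 to 3 levels and 15 to 25 minutes per level gives SD × √(2/31) × minutes, about 6 to 19 minutes. Every input is assumed, and the figure does not measure what adjustment for surgeon, gender and Cobb angle would recover.

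**Conclusion.** The point holds as an optional improvement in precision. The planned analysis of operative time is valid. It gives up whatever precision surgeon, gender and preoperative major Cobb angle could supply, and the significance-triggered covariate rule does not recover it.

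The size is conditional. The standard error would be roughly 7% to 20% smaller if these covariates explain 20% to 40% of the variance in time, with no gain below about 7%. This assumes analysis at 31 per arm and a fitting penalty of a few percent. The documents do not show where R² lies, so the gain is plausible but not demonstrated.

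**What to change.** Take operative time out of the group of variables given an unadjusted test, and add one sentence to the Data Analysis Plan:

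> Operative time (first incision to close) will be analysed by linear regression on treatment arm with surgeon, gender and preoperative major Cobb angle as prespecified covariates, reporting the adjusted difference with 95% CI; the Wilcoxon rank sum test will be kept as a sensitivity analysis for skewed times.

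Keep levels fused out of this model, and do not add a minutes-per-level analysis.

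The cost is three degrees of freedom (residual 60 to 57 with 62 subjects) and a slightly wider interval if the covariates turn out to explain almost nothing. No new data are needed, and nothing changes for patients or in the conduct of surgery. The sentence should be in place before any unblinded data are examined, which in practice means before the interim analysis. The same amendment could state whether procedure time is secondary or exploratory.
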